6.11.5.2 Days in ICU

‘Days in ICU’ will be summarized using descriptive statistics (n, mean, standard deviation, median, minimum and maximum) by treatment group.

‘Days in ICU’ will be the number of days in ICU up to Day 60. In this analysis the worst possible endpoint will be assigned to those subjects who died at any time up to Day 60. For subjects who died the days in ICU will be set to 60. Even for those who were never in the ICU. If

Controlled Quality Management Document			
	Sponsor:	Veru Inc.	
	Protocol Number:	V3011902	
STATISTICAL ANALYSIS PLAN. PHASE 2-3-4			

subject did not report any days in the ICU then their days will be set to zero except for those who died.

Same analysis will be performed in subgroups for region, standard of care and WHO Ordinal Scale at baseline.

A sensitivity analysis will be performed using the actual number of days in ICU. If subject was never in the ICU then days in ICU will be set to 0 even if subject died.

Treatment comparison will be based on analysis of covariance (ANCOVA) model including treatment as a factor, and study site (or country or region), remdesivir use (No/Yes), dexamethasone use (No/Yes) and WHO Ordinal Scale strata used in randomization as covariates. Treatment difference, standard error, 95% confidence interval and p-value will be presented.

Example SAS codes for the analysis are as follows:

```
proc mixed data=XXX order=internal;
  class trt01pn site remdesivir dexamethasone;
  model response=trt01pn site remdesivir dexamethasone whostrata /
    ddfm=kr;
  lsmeans trt01pn / cl diff;
  ods output tests3=tests lsmeans=lsmeans diff=diffs
  run;
```

6.11.5.3 WHO Ordinal Scale for Clinical Improvement change from baseline to Day 15, Day 22, and Day 29

WHO Ordinal Scale for Clinical Improvement will be summarized in frequency table by visit and treatment group.

Additionally, response status for each subject will be defined based on WHO Ordinal Scale for Clinical Improvement. This analysis will compare subjects that have WHO score 0 or 1 (responder) on the visit to subjects who have WHO score ≥ 2 (non-responder) on the visit.

Baseline for WHO Ordinal Scale is the last available record up to and including Day 1. If subject was discharged from the hospital prior to Day 15, 22 or 29 and WHO Ordinal Scale for Clinical Improvement is not collected or record is otherwise missing at those timepoints then the last available observation before or at the time of death/discharge will be carried forward. If subject dies then following time points will be set to the worst possible outcome (score=8).

Controlled Quality Management Document		
	Sponsor:	Veru Inc.
	Protocol Number:	V3011902
STATISTICAL ANALYSIS PLAN. PHASE 2-3-4		

The number and percentage of responders will be summarized by treatment group and visit.

Responders will be analyzed using similar logistic regression model except not planning multiple imputation as the above algorithm provides responder status for all subjects.

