## 9.3 Analysis Scope

The Intent-to-Treat (ITT) analysis scope will include all data collected from randomization to the end of the study at Day 60. This will be considered the primary analysis scope for the primary analysis.

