## 9.5 Secondary Endpoint

Primary analysis of secondary endpoints will be performed on the ITT analysis set and the ITT data scope regardless of patient's use of rescue medications, protocol violations or investigational product discontinuation consistent with the treatment policy strategy.

Full details for the handling of missing data, and consideration of subjects that die during the study for those endpoints that do not directly incorporate death, will be included in the Statistical Analysis Plan.

### 9.5.1 Proportion of patients alive and free of respiratory failure at Day 29, Day 15 and Day 22

Respiratory failure is defined as endotracheal intubation and mechanical ventilation, extracorporeal membrane oxygenation, high-flow nasal cannula oxygen delivery, noninvasive positive pressure ventilation, clinical diagnosis of respiratory failure with initiation of none of these measures only when clinical decision making is driven solely by resource limitation.

This analysis will compare the percentage of subjects that are alive without respiratory failure (responder) on Day 29 and on Day 15 and on Day 22.

Proportion of subjects alive and free of respiratory failure will be analyzed separately at each timepoint using the same logistic regression methodology as primary endpoint ([section 9.4.1](#)).

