#### 9.5.1.1 Days in ICU

Days in ICU will be summarized using descriptive statistics (n, mean, standard deviation, median, minimum, and maximum) by treatment group.

For subject who die, days in ICU will be set to the worst possible outcome (29 days) to give deaths unfavorable value in the analysis.

Treatment comparison will be based on analysis of covariance (ANCOVA) model including treatment as a factor and study site, gender, remdesivir use (No/Yes), dexamethasone use

(No/Yes) and WHO Ordinal Scale for Clinical Improvement at baseline as covariates. Treatment difference, standard error, 95% confidence interval and p-value will be presented.

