#### **9.5.1.3 Days on mechanical ventilation**

Days on mechanical ventilation will be summarized using descriptive statistics (n, mean, standard deviation, median, minimum and maximum) by treatment group.

For subject who die, days on mechanical ventilation will be set to the worst possible outcome (29 days) to give deaths unfavorable value in the analysis.

Days on mechanical ventilation will be analyzed using the same methodology as for Days in ICU ([section 9.5.1.2](#)).

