#### **9.5.1.4 Days in hospital**

Days in hospital will be summarized using descriptive statistics (n, mean, standard deviation, median, minimum and maximum) by treatment group.

For subject who die, days in hospital will be set to the worst possible outcome (29 days) to give deaths unfavorable value in the analysis.

Days in hospital will be analyzed using the same methodology as for Days in ICU ([section 9.5.1.2](#)).

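### Protocol scores a death as 29 days and the SAP as 60 for ICU, ventilation and hospital days; the visible SAP change list omits this, and the SAP's ANCOVA drops gender and fits WHO stratum as linear (minor)

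*SAP*

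**What the plan says.** **Death score, protocol.** Section 9.5.1.1: "For subject who die, days in ICU will be set to the worst possible outcome (29 days". Section 9.5.1.3: "days on mechanical ventilation will be set to the worst possible outcome (29 days". Section 9.5.1.4: "days in hospital will be set to the worst possible outcome (29 days". None of the three says over which days the count runs. Section 9.5 states: "Primary analysis of secondary endpoints will be performed on the ITT analysis set and the ITT data scope", and section 9.3 says that this scope "will include all data collected from randomization to the end of the study at Day 60". Section 9.5 also leaves to the SAP the full details on patients who die, for endpoints that do not themselves incorporate death.

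**Death score, SAP.** In 6.11.5.2 the ICU variable "will be the number of days in ICU up to Day 60". The score for a death follows: "For subjects who died the days in ICU will be set to 60". It applies to a death at any time up to Day 60, including in patients who never entered the ICU. Sections 6.11.5.4 (ventilation) and 6.11.5.5 (hospital) reuse the rule. The SAP adds: "A sensitivity analysis will be performed using the actual number of days in ICU".

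**Testing.** SAP 6.11.7 puts days in ICU and days on ventilation, and no other secondary endpoint, into a Holm procedure after the primary test.

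**Record of changes.** The visible text of SAP section 9 has three items: the randomization strata, the WHO-score analysis and Holm. Redacted blocks follow.

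**Model.** The protocol ANCOVA adjusts for site, gender, remdesivir, dexamethasone and baseline WHO score. The SAP text and code for the same ANCOVA have no gender term and use the randomization stratum for WHO. In the example PROC MIXED code, whostrata stands in MODEL but not in CLASS.

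**The concern.** Two current documents give different values for the same quantity. The score given to a death drives these endpoints whenever mortality differs between arms, and two of the three carry the only formal secondary tests in the SAP. A reader who starts from the protocol would expect 29, and would find nothing in the visible change list to say that it became 60 or why.

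The value 29 may also fail its own label. If days are counted to Day 60, a survivor with 30 or more ICU days scores worse than a patient who died.

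The covariate differences affect the same model. Gender is dropped without a visible explanation, and the stratification factor is coded differently from the SAP's other models.

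**Working it through.** **1. The plan's own figure.** The only sizing calculation is for Day 60 mortality (Protocol 9.1): 5% of 140 vs 25% of 70.

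SE = √(0.05×0.95/140 + 0.25×0.75/70) = 0.0549, so the interval is −0.20 ± 1.96×0.0549 = [−0.308, −0.092], as stated. Neither document gives a power calculation for the days endpoints.

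**2. Contribution of deaths alone.** With death score D and mortality p, deaths add D×(p_placebo − p_VERU) to the placebo-minus-VERU-111 difference.

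- D = 29: 29 × 0.20 = 5.8 days
- D = 60: 60 × 0.20 = 12.0 days

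The ratio is 60/29 = 2.07 at any mortality difference. This step needs no outside assumption.

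**3. Effect on the test.** With survivor mean m and SD s, the arm mean is pD + (1−p)m and the variance is (1−p)s² + p(1−p)(D−m)². The documents do not give m and s for this trial. Assume m = 5 and s = 8 in both arms, with 5% vs 25% mortality:

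| Score | Placebo mean | VERU-111 mean | Difference | SE | Power at 0.05 |
|---|---|---|---|---|---|
| 29 | 11.0 | 6.2 | 4.8 | 1.69 | 81% |
| 60 | 18.75 | 7.75 | 11.0 | 3.20 | 93% |

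The larger score raises both the difference and its SE, so power moves much less than the estimate.

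**4. How often a decision would differ.** This is a simulation of 140 vs 70 patients with mortality 5/25, 10/25, 15/25 and 15/30%, and 20,000 trials per setting (6,000 for the Phase 2 rows). Survivor ICU days are exponential, rounded up and capped. Half of ICU survivors are ventilated, for 70% of their ICU days. A pooled t-test stands in for the ANCOVA, and Holm follows SAP 6.11.7. Survivor ICU use is an assumption in every row. Entries are the share of trials passing the primary test in which at least one Holm claim differs between 29 and 60.

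| Survivor ICU use | Counted to Day 60 | Protocol read as Day 29 |
|---|---|---|
| 30% vs 40% ever in ICU, mean 7 vs 10 days | 0.3% to 3% | 0.3% to 3% |
| 20%, 8 days, both arms | 2% to 10% | 2% to 9% |
| 40%, 10 days, both arms | 12% to 23% | 8% to 20% |
| 60%, 12 days, both arms | 30% to 39% | 19% to 28% |
| Survivor means near Phase 2 (3.0 vs 9.6 days) | 0.1% to 0.3% | – |
| Phase 2 means with deaths assumed scored 29 | 2% to 9% | – |

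The last row backs survivor means out of the Phase 2 figures in Protocol 3.3 (1/19 and 6/20 deaths). VERU-111: (3.0 − 29/19)/(18/19) ≈ 1.6. Placebo: (9.6 − 29×0.30)/0.70 ≈ 1.3.

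An ANCOVA in place of the t-test (4,000 trials) gave 12% to 23% for the third row and 0.4% to 5% for the first. With equal mortality and equal ICU use, either score was significant at 0.05 in 4.7% to 5.0% of trials, so neither inflates the error rate. The direction is not fixed. With equal survivors, 60 usually gives more claims. With the first row's survivor benefit at 15% vs 25% mortality, days in ICU reached 0.025 in 58% of all trials with 29 and 47% with 60.

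**5. Is 29 the worst value?** It depends on the window, which the protocol does not state. If the Day 60 data scope is the window, a survivor can exceed a death by up to 60 − 29 = 31 days. Under the exponential assumption, exp(−29/10) = 5.5% to exp(−29/12) = 8.9% of survivor ICU stays pass 29 days. If a Day 29 window was meant, 29 is the maximum and the SAP changed both window and score.

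**6. Covariates.** SAP 6.11.1 and 6.11.3 list sex and whostrata in CLASS for the logistic, GENMOD and Cox models. The MIXED code in 6.11.5.2 lists neither, so whostrata enters as one slope over strata 4, 5 and 6. Under assumed strata of 45/45/10% and death odds ratios of 1/2.5/6 by stratum and 1.5 for males, dropping sex moves the estimate by 0.15 to 0.21 days on average and linear WHO by 0.14 to 0.19 days. Together they change a Holm claim in 0.1% to 6% of trials.

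**The case against.** The strongest reply is that the rule is settled. The protocol hands the details on deaths to the SAP. The SAP (30-JUN-2022) is later than protocol version 7.0 (18-MAR-2022), its window and score agree, and its actual-days analysis shows how much the result depends on the death score. All of this stands. A reader might infer that the analysis is undefined or that two rules compete; the documents do not support that.

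A reader might also take step 4 as the chance that the trial's formal conclusion is in doubt. It is not. The protocol has no Holm procedure, and its key secondary endpoint is being alive without respiratory failure at Day 29. Holm on ICU and ventilation days exists only in the SAP, which uses 60. No document combines Holm with 29, so the rates illustrate sensitivity to the score. The higher ones also need equal survivor use above the Phase 2 VERU-111 mean of 3.0 days (about 4.2 and 7.5 days in the 40% and 60% settings), although Phase 2 had 39 patients and its scoring of deaths is not stated.

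Third, one might say flatly that 29 is not the worst value. The data scope says which data count; it need not set a counting window, and the same scope covers the Day 15, 22 and 29 endpoints. A Day 29 window is possible, since Days 45 and 60 are telephone visits. The statement holds only on one reading.

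Finally, redacted text follows section 9, so only its visible part can be said to omit the change. The ANCOVA code is labelled as an example, but the missing gender term is in the SAP text as well.

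What survives is that the protocol did not leave the value open: it printed 29 three times. Replacing a stated value is a change of the kind that section 9 lists. The actual-days analysis does not address 29 versus 60, and no ANCOVA table listed in SAP 11.1 is described as using 29.

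**Conclusion.** The concern holds as a minor, unrecorded conflict between protocol and SAP, with two small model discrepancies. In practice 60 would be used.

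The firm figure is the deaths-only contribution, 5.8 against 12.0 days, which rests on the protocol's assumed 5% vs 25% mortality. The effect on a significance decision ranges from near 0% to about 39% over assumed survivor ICU use, and from 0.1% to 9% when anchored to the Phase 2 means. It illustrates sensitivity and is not an error rate of the plan. The covariate effects are small under the assumptions in step 6. The primary endpoint is unaffected.

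**What to change.** - In SAP 6.11.5.2, restore sex to the ANCOVA text, CLASS and MODEL, and add whostrata to CLASS. This uses two more model degrees of freedom: one for sex, and one for moving WHO stratum from a slope to three classes.
- State one counting window and one death score in both documents for all three endpoints. Day 60 and 60 match the SAP and also fit the protocol's data scope.
- Before unblinding, record in SAP section 9 the change from 29 to 60, and the use of the randomization stratum in place of the baseline WHO score.
- Correct the 29 in Protocol 9.5.1.1, 9.5.1.3 and 9.5.1.4 at the next amendment.

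The cost is SAP wording, two lines of SAS code and possibly the amendment process in Protocol 10.3. No new data are needed, since sex is collected and the strata are known.

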6.11 Efficacy Analyses

All statistical tests will be performed using a two-tailed 5% overall significance level, unless otherwise stated. All comparisons between treatments will be reported with 95% confidence intervals for the difference.

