6.11.5.4 Days on mechanical ventilation

Mechanical ventilation is defined as subject having ‘Intubation and mechanical ventilation’ or ‘Ventilation + additional organ support – pressors, RRT, ECMO’.

‘Days on mechanical ventilation’ will be summarized using descriptive statistics (n, mean, standard deviation, median, minimum and maximum) by treatment group.

‘Days on mechanical ventilation’ will be defined using two different algorithms similarly to ‘Days in ICU’.

‘Days on mechanical ventilation’ will be analyzed using the same methodology as for ‘Days in ICU’ and the same sensitivity analysis will be performed.

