6.11.7 Multiplicity

Holm (1979) step-down procedure will be used to control multiplicity for selected key secondary endpoints (days in ICU and days on mechanical ventilation).

If the primary analysis of the primary endpoint is significant at the <0.05 level key secondary endpoints days in ICU and days on mechanical ventilation will be tested using the Holm step-down procedure. In this way an overall type 1 (false-positive) error rate of 5% will be maintained so that no statistical significance for the key secondary efficacy endpoints will be claimed unless the principal analysis of the primary efficacy endpoint using the ITT set is statistically significant at the 5% level.

Holm procedure will be applied as follows:

1. If the p-value for primary endpoint ≥ 0.05 then testing will stop and key secondary endpoints will not be tested. If p-value <0.05 then testing continues to key secondary endpoints.
2. P-values for key secondary endpoints will be sorted from smallest to greatest (ascending order).
3. The smallest p-value for key secondary endpoints will be compared to 0.025.
4. If the smallest p-value yields significant result at 0.025 level then sequential testing continues to the next largest p-value and adjusted alpha value of 0.05. Otherwise the testing will stop.

Data from all analyses, regardless of the level of significance, will be presented for review.

Controlled Quality Management Document	
	Sponsor: Veru Inc.
	Protocol Number: V3011902
STATISTICAL ANALYSIS PLAN. PHASE 2-3-4	

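### As written, the SAP scores a living or untraced subject with no recorded ICU or ventilator days as 0, even when the later course is unknown, in the two Holm-tested days endpoints

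*SAP*

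**What the plan says.** Protocol 9.5 leaves the rules for the secondary endpoints to the SAP: "Full details for the handling of missing data, and consideration of subjects that die during the study" are to be given there.

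SAP 6.11.5.2 gives two scoring rules for days in ICU:

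- **Deaths in the 60-day period:** "For subjects who died the days in ICU will be set to 60. Even for those who were never in the ICU".
- **Everyone else with nothing recorded:** if a "subject did not report any days in the ICU then their days will be set to zero except for those who died".

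The sensitivity analysis in the same section uses actual days and adds: "If subject was never in the ICU then days in ICU will be set to 0 even if subject died".

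SAP 6.11.5.4 says that ventilator days "will be defined using two different algorithms similarly to" days in ICU, and 6.11.5.5 says the same of days in hospital. Under SAP 6.11.7, if mortality is significant, "key secondary endpoints days in ICU and days on mechanical ventilation will be tested using the Holm step-down procedure". The first step is at half of the 5% level: "The smallest p-value for key secondary endpoints will be compared to 0.025". Days in hospital is not in that procedure.

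The SAP treats incomplete follow-up differently elsewhere. For Day 60 mortality (6.11.1), subjects lost to follow-up are multiply imputed. For alive without respiratory failure (6.11.5.1), subjects of unknown vital status are multiply imputed.

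**The concern.** The zero rule does not separate two kinds of subject. One is followed to Day 60 and never enters the ICU, so 0 is a fact. The other leaves the study in hospital with the later course unknown, so 0 is a guess at the most favourable end of a 0 to 60 scale. For a subject lost after some ICU days the SAP gives no rule; the truncated count would presumably stand.

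The SAP foresees this group. Its mortality imputation model codes the discharge variable as no for subjects who withdraw before Day 60 without having been discharged. Such a subject can be imputed as dead in some of the 50 mortality data sets and still score 0, not 60, for ICU and ventilator days.

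Nothing planned would show the effect. The actual-days analysis changes only how deaths are scored, and every days table listed in SAP 11.1 is on the ITT set. At stake are the estimates and p-values of the only two secondary endpoints with a formal claim.

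**Working it through.** The plan gives no figure for this rule, so there is none to reproduce. The check sizes the effect.

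**Inputs from the documents.** 140 VERU-111 and 70 placebo subjects; planning mortality 5% and 25% (Protocol 9.1); Phase 2 mean ICU days 3.0 and 9.6 (Protocol 3.3); death scored 60 (SAP 6.11.5.2). Protocol 9.5.1.1 scores deaths at 29 days; the SAP value is used because the SAP rule is the one under review.

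**Assumptions.** All loss rates. The Phase 2 means are used as survivor means, for illustration. Lost subjects have the same expected score as the rest of their arm, and all of them are scored 0.

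**Formulas.** With mortality m and survivor mean s, the expected score is E = 60m + (1 − m)s. If a fraction l is lost and scored 0, the arm mean falls by l × E. The shift in the VERU-111 minus placebo difference is l_P × E_P − l_V × E_V. A negative shift favours VERU-111.

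**One subject.** A lost subject who in truth died moves the arm mean by 60/140 = 0.43 day on VERU-111, or 60/70 = 0.86 day on placebo.

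**No treatment effect** (m = 20%, s = 3.0 in both arms). E = 12 + 0.8 × 3.0 = 14.4 days.

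| Loss, VERU-111 / placebo | Shift (days) |
|---|---|
| 5% / 0% | −0.05 × 14.4 = −0.72 |
| 10% / 0% | −0.10 × 14.4 = −1.44 |
| 0% / 5% | +0.72 |
| 5% / 5% | 0 |

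**Planning mortality with Phase 2 means.** E_V = 3 + 0.95 × 3.0 = 5.85. E_P = 15 + 0.75 × 9.6 = 22.2. The true difference is −16.35 days.

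- Loss 8% / 3%: 0.03 × 22.2 − 0.08 × 5.85 = 0.67 − 0.47 = +0.20 day, against VERU-111.
- Loss 5% / 5%: 0.05 × 16.35 = +0.82 day, so the difference shrinks to −15.53.
- VERU-111 gains only if its loss rate exceeds 22.2/5.85 = 3.8 times the placebo rate.

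**Rejection rate with no effect.** Two-sample t-test at two-sided 0.025, 140 against 70, 5,000 replicates, survivor mean about 5 days:

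| Loss, VERU-111 / placebo | 20% mortality | 30% mortality |
|---|---|---|
| 0% / 0% | 0.024 | 0.026 |
| 5% / 5% | 0.025 | 0.028 |
| 5% / 0% | 0.031 | 0.036 |
| 10% / 0% | 0.047 | 0.048 |

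The Monte Carlo standard error near 0.025 is √(0.025 × 0.975/5000) = 0.002. These are rates for one ungated test without covariates.

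**The case against.** **The zero rule may only be meant to code a blank ICU log.** The SAP does not name lost subjects here, so the result follows from the wording and not from a stated intention. The point still stands: death is the only exception, and no other rule covers these subjects.

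**Follow-up is protected.** Stopping study drug does not end follow-up (Protocol 8.9), and vital status is sought by telephone or public records even after early termination (Protocol 8.10). A death found this way scores 60, which reduces the problem. It does not supply ICU or ventilator days: a subject found alive with none recorded still scores 0. If all vital status were recovered, what is missing is survivors' days; at 3.0 to 9.6 days each, a 5-point difference in loss is worth 0.15 to 0.48 day when both arms share the same mean.

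**The endpoints sit behind mortality.** They are tested only after a significant primary result. The rejection rates above are therefore not the trial's overall error rate. The distortion of the estimates remains.

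**Stronger readings are not supported.**

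- A reader might infer that the rule favours VERU-111, or whichever arm loses more subjects. That holds when the arms share the same expected score; at the planning figures, 8% against 3% loss works against VERU-111.
- A reader might infer that the confidence interval is too narrow because a guess is treated as observed. Interval width was not calculated, and with equal loss the simulated rejection rate stays near nominal.
- A reader might extend the zero rule to days in hospital. Subjects enter at WHO scores 4 to 6, all hospitalized, so it would essentially never apply. Only truncated counts are at issue there.

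**Conclusion.** The point holds as a gap in the scoring rule. As written, SAP 6.11.5.2 and 6.11.5.4 give the best score to subjects not known to have died whose ICU or ventilator course is unknown and who have no recorded days, and SAP 6.11.7 tests both endpoints formally. The missing-data detail that Protocol 9.5 promised is absent for them.

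The size rests on assumed loss rates. Under no effect, one-sided loss of 5% to 10% on VERU-111 is worth 0.7 to 1.4 days and raises rejection at nominal 0.025 to about 0.03 to 0.05. Equal loss gives no bias under no effect and dilutes a true benefit. At the planning figures the shifts shown are under 1 day against a difference of about 16 days. With loss low or vital status well traced, the effect is small. It should be corrected because the direction cannot be known in advance and the remedy is cheap.

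**What to change.** In SAP 6.11.5.2, and by reference in 6.11.5.4:

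1. Restrict the zero rule to subjects with no ICU (or ventilator) days who were followed to Day 60, or who have documented discharge and known vital status.
2. For the others, multiply impute unknown vital status with the primary-endpoint model: treatment, sex, site (or country or region), discharge, treatment discontinuation, remdesivir, dexamethasone and WHO strata. Score 60 if imputed dead.
3. If alive, or imputed alive, impute days with the same covariates, bounded below by days already observed and above by 60. Do this even when every vital status is known, because SAP 6.11.1 then skips its own imputation.
4. Run the ANCOVA in each imputed data set and pool by Rubin's rules.
5. Keep the current rule as a sensitivity analysis.

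For days in hospital, state how truncated counts are handled.

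The cost is SAP wording and one added imputation step. The mortality imputation model and its discharge variable already exist, and no new data are needed.

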## 9.0 STATISTICAL ANALYSIS

### 9.1 Sample Size Calculation

In the Phase 2, the VERU-111 treated group showed a 5.3% mortality rate compared to a 30% mortality rate in the Placebo group in the same patient population.

Approximately, 210 subjects are planned to be randomized at a 2:1 ratio into two treatment arms (140 subjects in the VERU-111 treated group and 70 subjects in the Placebo treated group). Randomization will be stratified by baseline WHO Ordinal Scale score of 4, 5 and 6 such that subjects with a WHO Ordinal Scale of 4, 5 and 6 at baseline will be approximately equally distributed between the treatment groups. Assuming a rate of mortality of 5% in the VERU-111 treated group and 25% in the Placebo treated group, the above sample sizes will yield 95% confidence interval of [-0.308, -0.092] for the risk difference between treatment groups. Other scenarios are shown in the table below.

$$\text{Confidence interval} = (p_1 - p_2) \pm z^* \sqrt{(p_1(1-p_1)/n_1 + p_2(1-p_2)/n_2)}$$

where:

- $p_1, p_2$ : sample 1 proportion, sample 2 proportion
- $z$ : the z-critical value based on the confidence level
- $n_1, n_2$ : sample 1 size, sample 2 size

Table of Alternative 95% Confidence intervals for the difference between Treatment Groups:  
 Mortality at Day 60

VERU-111	Placebo	Difference	LOWER 95% CI	UPPER 95% CI
0.05	0.15	-0.1	-0.191107629	-0.008892371
0.05	0.2	-0.15	-0.250420118	-0.049579882
0.05	0.25	-0.2	-0.307672652	-0.092327348
0.05	0.3	-0.25	-0.363261644	-0.136738356
0.1	0.15	-0.05	-0.147297482	0.047297482
0.1	0.2	-0.1	-0.206067903	0.006067903
0.1	0.25	-0.15	-0.262958399	-0.037041601
0.1	0.3	-0.2	-0.318297929	-0.081702071
0.15	0.15	0	-0.102449012	0.102449012
0.15	0.2	-0.05	-0.160812454	0.060812454
0.15	0.25	-0.1	-0.21742487	0.01742487
0.15	0.3	-0.15	-0.27256998	-0.02743002

With significance level  $\alpha=0.05$ , and a 2:1 ratio of enrollment into the VERU-111 and Placebo arms respectively, the sample size is adequate to achieve  $>92\%$  power assuming the treatment estimates stated above.

NOTE: The IDMC will monitor efficacy and safety and may make a recommendation to stop the study based on treatment success according to the statistical analysis plan and IDMC charter for this study.

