6.11.5.5 Days in hospital

‘Days in hospital’ will be summarized using descriptive statistics (n, mean, standard deviation, median, minimum and maximum) by treatment group.

‘Days in hospital’ will be defined using two different algorithms similarly to ‘Days in ICU’.

‘Days in hospital’ will be analyzed using the same methodology as for ‘Days in ICU’ and the same sensitivity analysis will be performed except the subgroup analyses will not be performed.

6.11.5.6 The proportion of subjects that die on study at Day 15, Day 22, and Day 29.

The number and percentage for all-cause mortality will be summarized by treatment group and visit.

These endpoints will be analyzed using the same methodology as for the primary endpoint (separate analysis will be performed for each visit):

- Multiple imputation + logistic regression model
- Risk differences between treatment groups (using identity link function).

Controlled Quality Management Document			
	Sponsor:	Veru Inc.	
	Protocol Number:	V3011902	
STATISTICAL ANALYSIS PLAN. PHASE 2-3-4			

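### The only planned sensitivity analysis of ICU, ventilator and hospital days compares actual days with no account of death, so it does not test whether the main result depends on scoring a death as 60

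*SAP*

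**What the plan says.** SAP 6.11.5.2 counts ICU days up to Day 60 and gives 60 to anyone who died by then, including those never admitted to the ICU. It then plans one sensitivity analysis, on actual ICU days: "If subject was never in the ICU then days in ICU will be set to 0 even if subject died". SAP 6.11.5.4 carries both scorings over to ventilator days, where "the same sensitivity analysis will be performed". SAP 6.11.5.5 does so for hospital days: "the same sensitivity analysis will be performed except the subgroup analyses will not be performed".

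The actual-days version is inferential. Tables 14.2.3.10, 14.2.5.10 and 14.2.6.10 are ANCOVAs, and SAP 6.11.5.2 asks for a treatment difference, confidence interval and p-value.

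ICU days and ventilator days are the two endpoints in the Holm procedure (SAP 6.11.7). That section does not name the scoring it uses, and the SAP does not say how a conflict between the two scorings would be read.

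The protocol (9.5.1.1, 9.5.1.3, 9.5.1.4) scores deaths at the unfavourable end, at 29 days rather than 60, and plans no actual-days comparison. Protocol 9.5 leaves the details of handling deaths to the SAP. SAP section 9 does not list the actual-days analysis among the changes.

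**The concern.** A score of 60 for death is a convention, and it drives much of the main result. A sensitivity analysis should show whether the conclusion survives another reasonable way of counting death against a treatment. This one stops counting death at all. A patient who dies early leaves few days on the counter, and a patient whom the drug keeps alive through a long stay leaves many. If the two versions disagree, the reader cannot tell whether the main result is fragile or whether the check is penalising survival.

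At stake is the reading of the supportive tables for both Holm-tested endpoints and for hospital days. A p-value labelled as a sensitivity result could count against a drug that lowers mortality as planned.

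**Working it through.** **1. Inputs.** From Protocol 9.1: "Approximately, 210 subjects are planned to be randomized at a 2:1 ratio into two treatment arms", that is 140 and 70; "Assuming a rate of mortality of 5% in the VERU-111 treated group and 25% in the Placebo treated group". From SAP 6.11: two-sided 5% tests. The documents give no ICU or ventilator days for patients who die, none for patients the drug would save, and no standard deviation or power for the days endpoints. All stay lengths below are assumptions.

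**2. The plan's own figure.** Protocol 9.1 says "the above sample sizes will yield 95% confidence interval of [-0.308, -0.092] for the risk difference between treatment groups". Standard error = √(0.05×0.95/140 + 0.25×0.75/70) = √(0.000339 + 0.002679) = 0.0549. Then −0.20 ± 1.96×0.0549 = [−0.308, −0.092]. It reproduces. Power at these rates is 97.5% (pooled z-test), consistent with the stated figure of more than 92%.

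**3. The two scorings, patient by patient (illustrative).**

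| Patient | Main score | Actual days |
|---|---|---|
| Dies Day 3, never in ICU | 60 | 0 |
| Survives, never in ICU | 0 | 0 |
| Dies after 5 ICU days | 60 | 5 |
| Survives after 20 ICU days | 20 | 20 |
| Dies after 15 ICU days | 60 | 15 |
| Survives after 8 ICU days | 8 | 8 |

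On actual days, the first death ties with the best survivor, and the first two deaths score better than the 20-day survivor. The 15-day death still scores worse than the 8-day survivor. The reversal is real but does not hold for every pair.

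**4. Effect on the mean.** Let pC = 0.25 and pT = 0.05 be the mortality rates, d the mean days of those who die, a the mean days of those the drug saves, and e the days the drug saves in other survivors. Then, VERU-111 minus placebo:

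- actual days: (pC − pT)(a − d) − (1 − pC)e = 0.20(a − d) − 0.75e
- death = 60: 0.20(a − 60) − 0.75e

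With e = 0:

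| d | a | Actual days | Death = 60 |
|---|---|---|---|
| 0 | 10 | +2.0 | −10.0 |
| 5 | 15 | +2.0 | −9.0 |
| 8 | 30 | +4.4 | −6.0 |
| 15 | 15 | 0.0 | −9.0 |
| 15 | 5 | −2.0 | −11.0 |

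Actual days count against the drug only if a − d > 0.75e/0.20 = 3.75e. If half of the other survivors use the ICU for a mean of 8 days (0.5×8 = 4.0) and the drug cuts this by 30%, then e = 1.2 and the threshold is 4.5 days.

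**5. Simulated significance** (140 versus 70, unadjusted t-test, other survivors as in step 4, gamma stays with CV 1, 1,500 trials per case):

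- d = 5, a = 15, e = 0: actual days +1.9, significantly against the drug in 31% of trials. Death = 60 gives −8.9, significant benefit in 87%.
- Same d and a, with the 30% cut: significant apparent harm in 10%.
- d = 15, a = 8, e = 0: actual days −1.3, significant apparent harm in 0.3%, significant benefit in 16%.

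A second grid assumed mean time to death 10 to 15 days, 70% of deaths in the ICU, 25% of other survivors in the ICU for a mean of 8 days, saved patients staying a mean of 10 to 25 days, and no other drug effect. It gave −0.1 to +3.5 days, with significant apparent harm in 3% to 64% of trials. Repeating that grid with a 30% cut in other survivors' days gave 1% to 48%. The shape of the stay distribution also matters: one case (death at 10 days, stay 20 days) gave 49% in one run and 36% with exponential stays.

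**6. A scoring that keeps death unfavourable.** On the second grid, days alive and out of ICU favoured VERU-111 by 6 to 9 days (significant in 57% to 92%), against 7 to 10 days (64% to 94%) for death = 60.

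**7. Phase 2 (Protocol 3.3).** Mean ventilator days were 5.4 on placebo and 1.6 on VERU-111, with 6/20 and 1/19 deaths. Six deaths at 29 days would alone give 6×29/20 = 8.7, above 5.4, so those deaths were not all scored at 29 or 60. The mean still favoured the drug. For ICU days (9.6 versus 3.0), a score of 29 cannot be ruled out this way, since 9.6 exceeds 8.7.

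**The case against.** The best defence is that actual days is the one planned comparison showing how much of the main difference comes from the death rule and how much from ICU use. Replacing it with days alive and out of ICU would largely repeat the main result, as step 6 shows. Mortality is reported in full elsewhere: the primary endpoint, Kaplan-Meier and Cox analyses, and deaths at Days 15, 22 and 29. The simulated harm depends on stay lengths that the documents do not give, the SAP model is an adjusted ANCOVA rather than a t-test, and the Phase 2 ventilator means point the other way.

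Most of this stands as a limit on size. The Phase 2 result comes from 39 patients in a post-hoc analysis that the protocol itself calls hypothesis generating, and it does not make the scoring valid. Wanting to see resource use is a good reason to describe actual days by vital status. It is not a reason to test them between arms as a check on an analysis whose purpose is to count death as bad.

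A reader might also infer that death generally ranks better than survival here, or that an effective drug will look harmful. Neither follows: step 3 shows pairs in the right order, and step 4 shows the sign depends on a, d and e.

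**Conclusion.** The point holds as a defect of the sensitivity analysis. Scoring actual days without regard to death does not test dependence on the value 60; it substitutes a quantity that death can improve. At 5% versus 25% mortality, the simulated difference is about 0 to +3.5 days against VERU-111, with significant apparent harm in about 1% to 64% of trials. These figures rest on assumed stay lengths and on unadjusted tests, and more extreme inputs go further. The difference favours the drug if saved patients have short stays or if other survivors' stays are shortened.

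A reader might infer that an efficacy claim is at risk, or that a drug causing early deaths could win on this check. The documents do not support that. SAP 6.11.5.2 presents death = 60 as the analysis, and SAP 6.11.7 tests the days endpoints only after a significant mortality result. The primary endpoint and the main analysis are not affected. The remaining gap is that 6.11.7 does not name the scoring. The change should be made because the supportive p-values can mislead.

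**What to change.** - In SAP 6.11.5.2, and by reference 6.11.5.4 and 6.11.5.5, replace the actual-days comparison with one that keeps death unfavourable without the value 60. Options are days alive and out of ICU (off ventilation, out of hospital) from Day 1 to Day 60, or a rank analysis with death ranked last.
- Keep actual days as descriptive resource use, shown separately for subjects who died and who survived, with no treatment p-value and a note that they cannot be interpreted without mortality.
- State in SAP 6.11.7 that the Holm tests use the death = 60 version.
- List the change in SAP section 9.

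Cost: SAP wording and reprogramming of Tables 14.2.3.9–10, 14.2.5.9–10 and 14.2.6.9–10. No new data are needed, since Protocol 8.10 already collects the date of death. The treatment p-value for actual resource use is lost. Days alive and out of ICU will track the main analysis closely, because mortality largely drives both.
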